## 1 How to Refer to This Document

## 2 Summary

Device(s) being tested:	POWER KNEE MAINSTREAM – Dynamic, a pre-market device comparing to users' current microprocessor-controlled knee (MPK). For simplification the device under evaluation in this Clinical Investigation will be referred to as "investigational device" throughout this document.	
Instruments and equipment:	6MWT, Borg scale, Amputee mobility predictor (AMPro), Plus-M (12 item), PEQ, PMQ, L-test, video, data logging by Össur Logic, in house questionnaire for amputee and CPO.	
Subjects recruited:	Inclusion criteria:	Exclusion criteria:
15-18 amputee subjects	50Kg < body weight < 116Kg	50Kg > body weight > 116Kg
Up to 5 CPO subjects	K3-K4 amputees with unilateral transfemoral amputation or Knee disarticulation	Bilateral amputees
	Allows for 37mm knee center height to dome of pyramid alignment	Users with socket problems
	Currently using a MPK or Power Knee	Users with co-morbidities in the contralateral limb, which affect their functional mobility
	Older than 18 years old	Younger than 18 years old
	No socket issues/changes in the last 6 weeks and no socket changes expected during the duration of the study period.	Users with stump pain
	Comfortable and stable socket fit	Users with cognitive impairment
	Willing and able to participate in the study and follow the protocol	Users not involved in other clinical tests and/or receiving treatment that the testing might affect.
Procedures:	This is a prospective two group cross-over study, within subject comparison. 3 study visits are planned for amputee subjects, with approximately 2-3 weeks between visits, and an optional fourth visit 8-12 weeks after the third visit. During the first visit subjects will be checked for inclusion/exclusion, consented and randomly	

	
assigned into two groups and Group 1 (transitioning to the investigational device) will perform functional tests (6MWT, L-test, Borg scale, AMPro) and answer questionnaires on the performance of their current prosthesis to provide baseline information. The Group 1 subjects will be fitted and trained on the investigational device and a recommended prosthetic foot which they will use as their prescribed prosthesis for 2-3 weeks until the second visit, the other half will stay on their prescribed prosthesis until the second visit.
 
During the second visit the subjects of Group 1 will perform the same functional tests as in the first visit (6MWT, L-test, Borg scale, AMPro) on the investigational device and answer questionnaires on the performance of the investigational device, and then return to their prescribed prosthesis. The Group 2 will perform the same tests/questionnaires on their prescribed prosthesis and then be fitted and trained on the investigational device and use it as their usual prosthesis for 2-3 weeks.
 
During the third visit all subject will repeat the tests and questionnaires on the prosthesis they are fitted with (Group1 on the prescribed and Group 2 on the investigational device). Subjects will have the option to use the investigational device for an additional 8-12 weeks, those who choose that will be fitted with the investigational device or will stay on it, depending in which they are in at this point. They will be booked for the fourth visit; they will be contacted via telephone 4-5 weeks later and asked to provide feedback on their experience with the device so far. Those that choose not to keep using the investigational device will be returned to their prescribed prosthesis.
 
During the fourth visit subjects will answer the same questionnaires and perform the same functional tests as the other visits. Data will be collected from the knee on activity. They will then be fitted back to their prescribed prosthesis.
 
End of study.
 
CPO subjects will answer a questionnaire on the ease of setup of the investigational device and provide feedback on the ease of setup of gait functions.
 
See Table 1 below.
								
--	---	--	--	--	--	--	--	--	--

Table 1 Summary of procedures and visits

Procedure/activity	Recruitment phase: 2-6 weeks prior to baseline	Group 1 visit 1: Baseline	Group 2 visit 1: Baseline	Group 1 visit 2: 2/3w F/U	Group 2 visit 2: 2/3w F/U	Group 1 visit 3: 4/6w F/U	Group 2 visit 3: 4/6w F/U	Visit 4 Optinal 8-12w F/U
Potential subjects identified, fitting inclusion/exclusion criteria, by PI from customer database	X							
PI calls potential subjects and pre-screens by telephone	X							
Subject signs ICF, randomization		X	X					
Fitting, Training		X			X			
Subject fills in questionnaires		X		X	X	X	X	X

Subject performs 6MWT w/Borg scale and L-test	X	X	X	X	X	X
PI prints out activity report from investigational device		X		X	X	
Subjects that choose to keep using the investigational device are given an appointment in 8-12 weeks from visit 3. Others are fitted with their prescribed prosthesis and end participation.			X	X		
All subjects still active are fitted back to their prescribed prosthesis, end of study.						X
CPO subjects provide feedback on fitting the investigational device	X		X			

### 3 Changes from Previous Revision

## 4 Abbreviations

---

6MWT	Six Minute Walk test
ADE	Adverse Device Effect
AE	Adverse Event
AMPRO	Amputee Mobility Predictor (prostheses users)
BL	Baseline
CA	Competent Authority
CEP	Clinical Evaluation Plan
CER	Clinical Evaluation Report
CI	Co-Investigator
CIB	Clinical Investigator's Brochure
CIP	Clinical Investigation Plan
CIR	Clinical Investigation Report
CRF	Case Report Form
CT	Clinical Trial
EC	Ethics Committee (see IEC, IRB, REB and REC)
FU	Follow-Up
ICF	Informed Consent Form
IDMF	Investigational Device Management Form
IEC	Independent Ethics Committee
IFU	Instructions For Use
IRB	Independent/Institutional Review Board
LCI	Local Co-Investigator
LPI	Local Principal Investigator
LRA	Local Research Assistant
PEQ	Prostheses Evaluation Questionnaire
PI	Principle Investigator
PIS	Participant Information Sheet
PKM	Power Knee Mainstream
REB	Research Ethics Board
REC	Research Ethics Committee
SAE	Serious Adverse Event
SADE	Serious Adverse Device Event
SOP	Standard Operating Procedure
SOTA	State-Of-The-Art
SRA	Sponsor Research Assistant
USADE	Unanticipated Serious Adverse Device Effect

## 5 Investigational Device

[figure not shown]
See Table 2 for details on the investigational device.

**Table 2 Identification and Description of the Investigational Device**

[figure not shown]
Summary description of the investigational device and its intended purpose:	
The investigational device is a motor driven microprocessor-controlled prosthetic knee, intended for moderate to high active transfemoral or knee disarticulation amputees. It provides support in locomotion tasks as well as non-cyclical tasks through powered flexion and extension.
 
The investigational device is used with a smart app to adjust and interact with the knee.

Manufacturer of the investigational device:	Össur ehf. [name]
Name or number of the model/type, including software version and accessories, if any, to permit full identification:	POWER KNEE MAINSTREAM – Dynamic (No product number yet, software version not available yet) Accessories: Lithium Ion Battery pack (no product number yet) Össur Logic is an iOS smart app and it is required to adjust and interact with the knee. It is a standalone software as a medical device, used with other bionic devices as well, the app is documented separately, see [1].
Traceability during and after the investigation:	Investigation Device Management Form (IDMF) will be used to track the use of each device within the clinical investigation using the device serial number.
Intended purpose of the investigational device in the proposed clinical investigation:	Intended purpose of the investigational device in the proposed clinical investigation is within the intended use as described below. See following chapters on the intended purpose of the investigational device in the proposed clinical investigation for details.
The populations and indications for which the investigational device is intended:	Unilateral transfemoral / knee disarticulation amputation Bi lateral transfemoral /knee disarticulation amputation Targeted Medical Indications: Any medical reasons resulting in amputation at or above the knee level.
Description of the investigational device:	POWER KNEE MAINSTREAM - Dynamic is composed of a motorized knee prosthesis, which forms the core of the system, as well as other devices used to sustain operation on a daily basis. More specifically, POWER KNEE MAINSTREAM – Dynamic is composed of four devices. Operation of the motorized knee prosthesis relies on a detachable battery pack, which provides system power, and a Prosthesis Configuration Device (software application) that allows adjustment of the knee parameters to optimize its performance with respect to the user physiological characteristics, activity level, gait style and personal preferences. Furthermore, the battery pack is provided and an off-the-shelf power supply, allowing conveniently recharging the battery pack when not used in the knee prosthesis. POWER KNEE MAINSTREAM - Dynamic is intended for moderately and highly active amputees (K3 to K4) of moderate/high impact levels, building on established powered knee technology and utilizing the clinical benefits associated with powered prosthetics. The system should not impose any activity limitations and should be designed for ease of use of K3 and K4 users. The device is a non-invasive, single patient, reusable system. The system is not used in direct contact with the body. It should be noted that the aspect of the prosthesis

	
that is in direct physical contact with the amputee is the liner/socket, to which the POWER KNEE MAINSTREAM - Dynamic is connected to. In other words, the POWER KNEE MAINSTREAM - Dynamic is not in direct physical contact with the amputee. An amputee typically wears prosthesis and thereby utilizes the POWER KNEE MAINSTREAM - Dynamic, for up to 18 hours a day over duration of multiple years.
 
The device will be supplied in a hard-plastic case with custom made foam cut-outs to protect the product and all relevant documents and accessories.
 
The devices will be labelled according to regulations concerning non-CE marked investigational devices. R&D engineers will be responsible for identification of devices: on the required label for each device will be a serial number, same format as those used for CE-marked Össur devices of a similar type.
 
Investigation Device Management Form (IDMF) will be used to track the use of each device within the clinical investigation using the device serial number.
 
Intended Use:
 
The POWER KNEE MAINSTREAM - Dynamic is intended to fulfil the requirements associated with daily ambulation of individuals showing an average to high activity level. The product targets an amputee population that are trans- femoral unilateral amputees showing good control over their residual limb with respect to the locomotion task range that they intend to address. Based on the user activity level, stump capacity and personal preferences, the product can be configured as a walking-only product or support the complete range of locomotion tasks introduced below. While being optimized for average users, the product can be used by amputees with a body mass ranging from 50kg to 116kg, as long as the maximum assistance and support levels provided by the motorized prosthesis are shown sufficient to sustain the safe product usage.
 
The following paragraphs provide more details on the product intended typical use for the various supported locomotion tasks.
 
Locomotion Tasks:
 
POWER KNEE MAINSTREAM - Dynamic provides complete support of the most commonly encountered locomotion tasks in daily living. Moreover, in order to properly address the requirements of a wide range of user activity levels, residual limb control and strength, the product allows the user-specific configuration of the product features, such that optimal performance and safety can be achieved on a user-specific basis. The following paragraphs provide more details on the supported locomotion tasks.
 
Walking: The POWER KNEE MAINSTREAM - Dynamic sustains typical level walking through stance-phase flexion control and swing phase kinematics restoring, while contributing to the overall user forward progression. Automatic cadence adjustment, as well as heel rise control, is provided in order to optimize the product performance with respect to the user needs and personal preferences.
 
Stairs Ascent: The POWER KNEE MAINSTREAM - Dynamic sustains step-over-step stairs ascent for intended users by providing mechanical assistance in the push-off phase and swing phase kinematics in order to favour proper and timely foot placement. For users showing limited residual limb control and strength, it is possible to block this locomotion task.
 
Stairs Descent: The POWER KNEE MAINSTREAM - Dynamic sustains step-over-step stairs descent for intended users by providing mechanical support in the controlled lowering phase of the gait cycle, while again focusing on kinematics and foot placement during the swing phase.
 
Inclined Planes: The POWER KNEE MAINSTREAM - Dynamic can be used on inclined planes ascent and descent for intended users. Again, the product provides assistance and/or support as per configured for each specific task, while proper

--	--

[figure not shown]
	
kinematics and foot placement represent the focus of the swing phase.
 
Non-cyclical Tasks: The POWER KNEE MAINSTREAM - Dynamic provides either support, assistance, or remains passive for tasks such as standing, sitting, sit-to-stand transfer, stand-to-sit transfer, and kneeling.
 
Operational Environment
 
POWER KNEE MAINSTREAM – Dynamic device is intended for use in indoor and outdoor environments, in common daily living environments, like home, office, and public location. POWER KNEE MAINSTREAM – Dynamic device is intended to support typical use in commonly encountered weather conditions, like rain, fog, cold, etc.
 
Product Configuration
 
The product is intended to be used with Ossur's standard prosthetic components. It is configured with standard proximal and distal connectors, allowing use with most commonly encountered socket technologies and shank replacement products. Foreseen ankle-foot products to be used with this product are Ossur's Pro-Flex pivot, Pro Flex XC and/or Pro-Flex LP.
 
The device does not incorporate, as an integral part, a substance or human blood derivative referred to in Section 7.4 of Annex I of 93/42/EEC, amended by 2005/50/EEC. It is manufactured without utilizing tissues of animal origin as referred to in Directive 2003/32/EC. Training requirements for subjects and procedures relating to fitting and use of a device will for all general purposes be similar to the training and procedures required for using a CE- marked device of a similar type.
 
POWER KNEE MAINSTREAM - Dynamic is a microprocessor controlled prosthetic knee. It is used exclusively for exo- prosthetic fitting of transfemoral and knee disarticulation amputees. It is utilized as part of prosthetic limb system, in other words an amputee requires additional components, such as a foot, to use the POWER KNEE MAINSTREAM - Dynamic in a functioning prosthesis. The POWER KNEE MAINSTREAM - Dynamic requires a certified prosthetist to set-up and fit the device to an amputee. The certified prosthetist uses software called "OssurLOGIC" running on a computer to communicate to the POWER KNEE MAINSTREAM - Dynamic, such that parameters can be optimized for an amputee. As the POWER KNEE MAINSTREAM - Dynamic is battery powered (rechargeable lithium ion) a charger is required.
 
The device is classified as ASSEMBLY, KNEE/SHANK/ANKLE/FOOT, EXTERNAL according to Title 21 §890.3500, bearing the product code ISW: "External assembled lower limb prosthesis.". It is 510(k) and GPM exempt, except for general requirements.

--	---

**Figure 1, Knee center height**

**Figure 2, POWER KNEE MAINSTREAM - Dynamic**

Summary of the necessary training and experience needed to use the investigational device:	Training requirements for subjects and procedures relating to fitting and use of a device will for all general purposes be equivalent to the training and procedures required for using a device of a similar type. The device should be supplied and fitted by a certified CPO.
Specific medical or surgical procedures involved in the use of the investigational device:	N/A

## 6 Justification for the Design of the Clinical Investigation

The introduction of microprocessor controlled prosthetic knee in 1997 was a major leap in prosthetics in restoring function and increase safety of individuals with a lower limb amputation. Countless studies showed the benefits of such devices, e.g. Hafner et al. and Bellmann et al.. However, such devices are still passive with a major shortcoming, which is that they cannot provide positive power to support the user. In other words, they are unable to generate concentric moments to support the user in situations in which such moments are needed. Standing up and step over step stair climbing are two examples where concentric moments are in principal needed, in order to fulfil these tasks. Although recent passive microprocessor controlled prosthetic knees have been introduced that offer modes which facilitate step over step stair climbing, the power needed still has to be generated by the proximal hip joint of the user. Especially in individuals with a trans-femoral amputation, who may have reduced all over physical capabilities, such modes cannot be used, due to the physical limitations of the user. This fact is for example substantiated by the inclusion criteria in Bellmann et al., who investigated step by step stair climbing in K-Level 3-4 subjects with a passive microprocessor controlled prosthetic knee. Beside in these rather complex movement patterns, knee power is also needed for knee flexion in the swing phase while walking. Although the magnitude of the power needed in this state is rather small, providing power has a pronounced clinical impact, since a reduced clearance in swing is associated with a higher risk of falls.

Several studies have provided evidence for the clinical performance of previous versions of the Power knee (PK), which has the same function and intended use, those are detailed in the Literature review device report [3].

Results of studies on previous versions of the Power knee indicate that the PK provides support in the sit to stand and stand to sit activity, provides stance phase flexion in level ground walking, support in ascending and descending ramps and stairs and that it does provide active flexion and extension during walking which leads to users being able to walk further and feel less tired. In addition, Pasquina et al. tested the Power Knee as an initial knee prosthesis after combat-related TF amputation or knee disarticulation and found indications that the Power Knee can be helpful as initial prosthesis after TF/KD amputation, participants reached mobility milestones faster than norms identified by expert panel. Shortening the rehabilitation time after amputation has the potential for great savings in healthcare expenditure and large benefits for the patients, e.g. with earlier mobilization and independence. Creylman et al. compared the Power knee and the Rheo knee (passive MPK), their results indicated more symmetric gait with the PK compared to passive MPK.

As the literature shows, a powered prosthetic knee which is able to generate concentric moments is of high interest, to better counterbalance the disability of individuals with a lower limb amputation.

### Preclinical testing

[figure not shown]
Variety of tests and activities have been carried out to verify the safety and performance of the investigational device. Structural test summary is presented in **20 Annex**.

Based on the intended use of the device, as it is not intended to be used directly on skin, the outcome of the risk analysis and that vendors have supplied verification that the device contains no Materials of Concern, biocompatibility testing was not necessitated.

Based on the results of these tests, calculations, specifications, and design verification and validation activities it is considered justifiable to use the device in human subjects.

### Existing clinical data

No clinical data exists for the investigational device.

[figure not shown]
A large black rectangular box that appears to be a redaction of sensitive information.

The data represented in the PMS report was gathered from Ossur's complaint and service system. Information from field reports (Weekly AM Reports from Ossur Americas) were used to track user and customer feedback over time. [2]

## 7 Objectives and Hypotheses

The primary objective of this study is to evaluate the efficacy of the investigational device in reducing exertion during walking compared to passive MPKs.

Additionally to evaluate the efficacy of the investigational device in the short and long term compared to passive MPKs and previous versions of the Power Knee, during daily living activities i.e. walking on level ground, in stairs and inclines, rising from and sitting down to a chair as well as performance of gait functions and ease of set up for average to highly active transfemoral/knee disarticulation amputees and CPOs.

No risks or anticipated adverse device effects (ADE) are to be assessed. Any side-effects occurring will be documented.

The hypotheses and endpoints are specified in Table 4.

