L	The investigational device provides ease of use of gait functions no worse than previous device	Self-report: PMQ (Questions 1 and 3-6) Likert scale 0-4  Objective measure L-test	Total score of PMQ questions 1, 3-6.  Proportion of subjects (p) successfully completing the L-test using gait functions.	For PMQ score: $H_0: \mu_1 \geq \mu_2 +  M_{NI} $ $H_1: \mu_1 < \mu_2 +  M_{NI} $ $ M_{NI}  = 2,5$ $p < 0.05$  For L-test: $H_0: p < 80\%$ $H_1: p \geq 80\%$ $p < 0.05$
M	Side effects N/A	Side effects	Occurrence of side effects	N/A

N	Mobility using the investigational device is no worse than with the comparator	PMQ total score (0-48)	Average total score of the PMQ	$H_0: \mu_1 \geq \mu_2 +  M_{NI} $ $H_1: \mu_1 < \mu_2 +  M_{NI} $ $ M_{NI}  = 5,5$ $p < 0.05$
O	Activity level increases with longer adaptation period on the investigational device	Activity reports from the knee (daily steps, use time)	Activity level after 8-12w follow up compared to 2w follow up on investigational device	$H_0: \mu_2 \geq \mu_3$ $H_1: \mu_2 < \mu_3$ $p < 0.05$

Informative endpoint: In house usability questionnaire (Perceived weight, size, look, ergonomics, fit w/clothes, battery life, preference, falls questionnaire)

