#### Visit 3:

During the third visit all subject will repeat the tests and questionnaires on the prosthesis they are fitted with. Subjects will have the option to use the investigational device for an additional 8-12 weeks, those who choose that will be fitted with the investigational device or stay on it, depending on which they are fitted with. They will be given an appointment for the fourth visit 8-12 weeks later. They will be contacted via telephone 4-5 weeks later and asked to provide feedback on their experience with the device so far, see script in **Appendix 18.1**. Those that choose not to keep using the investigational device will be fitted back on their prescribed prosthesis and end their participation in the study at visit 3.

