## 13 Ethical Considerations

### 13.1 Anticipated clinical benefits

A patient using the investigational device may or may not benefit clinically from using the device as opposed to using another **MPK prosthesis** commercially available. Compared to not using a **MPK prosthesis** the patient will benefit significantly in terms of mobility and ability to live independently. Further on the user will be trained on a new prosthetic component to experience the unprecedented functionality of the new component to mitigate the known deficiencies associated with his amputation. Within the test he/she will be trained on restoring physiological movement pattern closer to those of non-amputees.

Anticipated benefits include, among others: improved step-over-step ramp navigation; reduced effort to sit/stand and reduce likelihood of falls. See chapter 6 for details.

Additionally, the benefit for the user during the testing is that he/she helps in developing a new **MPK prosthesis**.

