### 14.2 Reporting procedures

Adverse events and device deficiencies are recorded and reported to the competent authority in all countries in which the trial is being conducted according to national guidelines.

All device related adverse events will be investigated. Adverse events that are serious, unanticipated and (possibly) device related shall be reported to the sponsor by telephone as soon as possible. The complete adverse event investigation form shall be faxed to the sponsor within 24 hrs. Within ten days the Sponsor will report to the IRB and the FDA. Any serious device related adverse event will lead to the immediate termination of the trial.

Participants will be provided the contact information of the investigator and told to call them in the event of an adverse event that may be connected to previous use of the device.

The Principal investigator shall supply a copy of the complete adverse event investigation form, together with a cover letter to the IRB when events are judged to be serious, unanticipated and (possibly) device related.

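### Section 7 disclaims assessment of risks that Table 4 and Section 14.2 say are collected, and no prespecified summary sets falls and other harms side by side for device and comparator

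*Combined protocol and SAP*

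**What the plan says.** Section 7 (Objectives and Hypotheses) states: "No risks or anticipated adverse device effects (ADE) are to be assessed. Any side-effects occurring will be documented".

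Table 4 nevertheless has a side-effects row (the second row labelled M) with occurrence as the endpoint and N/A for both hypothesis and acceptance criterion. Falls appear only in the informative line beneath the table, in a list that reads "Perceived weight, size, look, ergonomics, fit w/clothes, battery life, preference, falls questionnaire". Rows D, E and H test perceived safety for non-inferiority, with a margin of 1 on a 1-10 scale.

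Section 14.2 has adverse events and device deficiencies recorded and reported, and adds: "All device related adverse events will be investigated". It also says participants will be told to call the investigator about an adverse event that could be linked to earlier use of the device. Section 14.1 defines an adverse event without regard to its relation to the device.

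Section 13.1 names among the anticipated benefits "reduced effort to sit/stand and reduce likelihood of falls". Section 6 says "No clinical data exists for the investigational device", while citing studies of earlier Power Knee versions.

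For the optional extension, Section 8.4 (Visit 3) says: "They will be contacted via telephone 4-5 weeks later and asked to provide feedback on their experience with the device so far". The script for that call is in an appendix that was not available for this review.

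**The concern.** An analyst who follows Section 7 has no mandate to summarise harms, and one who follows Section 14.2 has records but no instruction on how to present them. The report could then show perceived safety as no worse on rows D, E and H without setting reported falls on the device beside reported falls on the comparator. This is the device's first clinical study, and Section 6 itself ties swing clearance to fall risk, so readers will look for those counts.

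The call-in instruction adds a problem of capture. Participants decide whether an event might be connected to the device before they report it. In Group 2's comparator period there has been no use of the investigational device in the study, so taken literally the instruction covers none of those events. Any by-device table that draws on such calls would be fed unevenly.

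**Working it through.** **Passages side by side**

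1. Section 7 says anticipated adverse device effects are not assessed. By the Section 14.1 definition these are device-related adverse events, and Section 14.2 says all device-related adverse events are investigated. Read literally, both cannot be followed.
2. Sections 13.2 and 14 say the hazard analysis lists anticipated effects with their likely incidence. No planned output sets observed occurrence against that list.
3. Section 10.1 tests the Table 4 hypotheses. The side-effects row has no hypothesis and falls have no row. Sections 10.2 and 10.3 cover sample size, interim analysis, deviations and dropouts. None gives a summary of falls, side effects, adverse events or device deficiencies.
4. Section 8.4(iii) has the same questionnaires completed at three to four time points, and Table 6 places them at visits on both prostheses. Falls data on the comparator should therefore exist, although the questionnaire text could not be checked.

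**Share of device exposure in the extension**

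Inputs from Section 8.4: crossover device period 2-3 weeks, extension 8-12 weeks. Share = extension / (crossover device period + extension).

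- Lowest: 8 / (3 + 8) = 8/11 = 73%
- Highest: 12 / (2 + 12) = 12/14 = 86%
- Both at minimum or both at maximum: 8/10 = 12/15 = 80%

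**What the sample size can support**

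The documents give no figure for harms. Their one computed design figure, in Section 10.2, reproduces: n_eff = 15 × 3/π = 14.324; df = n_eff − 1 = 13.324; δ = 0.7084529 × √14.324 = 2.681; one-sided critical t = 1.768; power = 0.815. This concerns the Borg endpoint and matters here only because it fixes the study at 15 to 18 subjects.

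Upper bound on the proportion of subjects affected if none is, 1 − α^(1/n):

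| | n = 15 | n = 18 |
|---|---|---|
| One-sided 95%: 1 − 0.05^(1/n) | 18.1% | 15.3% |
| Upper limit of two-sided 95%: 1 − 0.025^(1/n) | 21.8% | 18.5% |

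Probability of seeing at least one affected subject, 1 − (1 − r)^n, at assumed true proportions r:

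| r (assumed) | n = 15 | n = 18 |
|---|---|---|
| 1% | 14% | 17% |
| 5% | 54% | 60% |
| 10% | 79% | 85% |
| 20% | 96% | 98% |

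Power of an exact two-sided paired (McNemar) test at 0.05 on the proportion of subjects who fall. The rates are assumed and the two periods are taken as independent within subject, so the discordant probabilities are p_c(1 − p_i) and p_i(1 − p_c), where p_c is the comparator rate and p_i the device rate:

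| Comparator vs device (assumed) | n = 15 | n = 18 |
|---|---|---|
| 20% vs 10% | 1.7% | 3.1% |
| 30% vs 15% | 5.3% | 8.0% |
| 40% vs 20% | 10.0% | 13.9% |

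A descriptive table is feasible. A confirmatory falls comparison is not.

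**The case against.** The Section 7 sentence stands under objectives and can be read as saying only that no risk hypothesis is tested, since its second half promises that side effects are documented. N/A is an ordinary acceptance criterion for a descriptive endpoint. Section 14.2 requires recording whatever the relatedness, Section 14.3 weighs serious device effects against benefit, and Section 10.3 says no particular information is excluded from analysis. An injurious fall is already an adverse event under Section 14.1. Much of this stands, and it rules out several stronger readings:

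- A reader might infer that the harm data cannot inform the risk-benefit view, or that falls will never be compared. Nothing bars either; what is missing is a prespecified summary.
- A reader might infer that participants may report only suspected device-related events. Section 14.2 does not say that this is the sole route, and the consent pages were not available.
- A reader might take 80% as the extension's fixed share, or total the extension exposure as if everyone opts in. The stated ranges give 73% to 86%, and no uptake figure is given.
- A reader might infer that Visit 4 relies on 8-12 weeks of recall, or that the planned call omits falls. Neither the questionnaire's recall window nor the call script could be seen.
- A reader might infer that better reporting would test the falls benefit in Section 13.1 or the risk-benefit statement in Section 13.5. Fifteen to 18 subjects cannot test a falls benefit, and Section 13.5 is an advance rationale resting on design verification and risk management.

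The lenient reading of Section 7 softens the contradiction but does not supply the missing summary. The safeguards in Section 14.3 and the urgent reporting in Section 14.2 concern serious events, so a non-serious fall would trigger neither.

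**Conclusion.** The point holds as an inconsistency plus a gap in planned reporting. Section 7 conflicts with Table 4 and Section 14.2. No prespecified summary sets falls, side effects, adverse device effects and device deficiencies side by side for device and comparator. The call-in wording in Section 14.2 risks under-reporting, especially in comparator periods; its size cannot be estimated from the documents.

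The primary Borg analysis is unaffected. What is at stake is whether the first clinical study of this device reports harms in an orderly way beside the benefits it claims. The change should be made, but the existing records are not unusable without it. The 73% to 86% share applies only to subjects who opt in. The power figures rest on assumed fall rates and independence between periods; the zero-event bounds rest only on the number of subjects. The redacted part of Section 6 may hold further safety background, which could not be judged.

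**What to change.** 1. Replace the Section 7 sentence with a descriptive safety objective: falls, side effects, adverse events and device effects, and device deficiencies, reported by device as event counts, subjects affected and weeks of exposure, with exact 95% intervals. Show the two crossover periods within subject (comparator period ending at Visit 3 for Group 1 and Visit 2 for Group 2) and the extension separately. State that no powered falls test is planned and that no claim of a tested falls benefit will be made. Cross-refer from Table 4 and Section 10.
2. Have the investigator classify each reported fall on the device against the Section 14.1 definitions.
3. In Section 14.2, tell participants to report any adverse event on either prosthesis, and leave relatedness to the investigator.
4. Use the existing side-effects and falls questionnaires (Appendix 2, items 8 and 10) at the planned 4-5 week call, unless its script already covers them. Check the script and questionnaire texts first.

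The cost is wording in Sections 7, 8.4, 10 and 14.2 and Table 4, one descriptive table, a slightly longer call and more unrelated events to log. No new visit, instrument or staff is needed.
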